***Measures, survey instruments and questionnaires, (including the collection of demographic data).***

**Baseline, Process, and Outcome Measurements (Table 2)**

All of the BNP measures (visual analogue pain scale and Brief Pain Inventory short form), pain coping (Coping Strategies Questionnaire), BF specific factors including demographics, ongoing BF assessment and algorithm, Breastfeeding Self-Efficacy Scale, maternal assessment of infant BF behaviors, maternal well-being symptoms [PROMIS anxiety, sleep, fatigue, perceived stress], Edinburgh Postnatal Depression Scale, perceived well-being [PROMIS global health], pain sensitivity SNPs, and quantitative sensory testing, were successfully collected in the pilot. The effect of the *BSM* intervention on pain self-efficacy, will be measured by the Self-Efficacy for Managing Chronic Illnesses Scale, the Index of Self-Regulation, and on maternal self-efficacy the Karitane Parenting Confidence Scale and Postpartum Bonding Instrument.

**IFSMT Context variables.**

**Breastfeeding Specific Factors, Physical and Social Environment, Individual and Family Factors and Biomedical Research Informatics**

**Computing System Demographics** The

questionnaires will be used to collect participants' demographics (age, gender, height, weight, race/ethnicity, education, socioeconomic and employment status), BF and medical history (parity, prior BF experience, route of delivery, baseline BNP knowledge, chronic conditions and medication usage), physical and social environment targeting BF support (hospital and home access to professional lactation support, and infant and family characteristics).

**Pain Sensitivity. Pain and Coping.** The Coping Strategies Questionnaire-Revised will assess participants' pain coping strategies (praying, coping self-statement, distancing from the pain, ignoring pain, catastrophizing, and distraction). Participants use a 7-point Likert scale to rate the **frequency** of their use of each coping strategy, "never do that" to "always do that" and its perceived control over their pain. Scores range from 7-42, with higher scores indicating more frequent use of the coping strategy.

**Peripheral and Central Pain Sensitivity.** Peripheral and central sensitivity will be measured using a standardized quantitative sensory testing battery of *cutaneous mechanical pain sensitivity*, involving measures of threshold, ratings of suprathreshold stimuli, temporal summation and after sensations, and pressure pain thresholds using the participant's non-dominant forearm. The testing battery and equipment will match those used by the gold standard German Neuropathic Pain Network. The testing assesses inadequate function (hypoalgesia) as well as gain of function (hyperalgesia) and results are evaluated using age- and gender-matched reference data in pain and control populations. Inter-rater reliability of the *quantitative sensory testing protocol* has been reported in several pain clinical trials, with each individual test demonstrating acceptable correlation coefficients.

**Candidate pain sensitivity SNPs genotyping.** Blood and/or buccal cell samples will be collected at baseline before discharge. Blood will be drawn by trained hospital staff or members of the research team before discharge in the patient's hospital room. At the 6 week and 24 week follow up, blood will be drawn at HH in the lactation room. At the follow up appointments at WAHS, the PROMPT research team member will escort participant to the phlebotomy area. At UCHC, the blood will be drawn at UConn Health BBL or Clinical Research Center. The research team will endeavor to have the blood drawn during routine clinical blood draws. Samples will be transported to the School of Nursing Biobehavioral lab, UConn lab service center or [name] lab to be processed, and split, volume permitting, for liquid N2 storage of a white-blood-cell pellet for later RNA studies. DNA will be isolated using the Qiagen DNA Easy Kit and QC'd prior to delivery of 500 ng to the lab service centers at the University of Connecticut, such as Center for Genome Innovation (CGI), Microbial Analysis, Resources and Services (MARS) or the School of Nursing Associated Laboratories. Samples will be batched in groups of 10 for processing on The Illumina Methylation EPIC Bead Chip.

For buccal cell swabs, participants will be instructed to rinse their mouth with clean water and roll the sterile buccal brush firmly on the inside of both cheeks. The participant will roll one brush for 60 seconds on the first cheek and repeat again on the second cheek. Samples will be transported to the SON biobehavioral lab and stored at -80°C until processing in batches at a UConn lab service center or shipped to [name] lab for verification of results. Genomic DNA (gDNA) will be isolated from buccal samples using the OMNIgene•ORAL OMR-110). The samples are stable at room temperature for 30 days, allowing transport to the SON biobehavioral lab, UConn lab service center, and/or

Time Points Module	Item#	α	T1	T2	T3	T4	T5	T6	T7	T8	T9
Context factors:											
Breastfeeding Specific Factors  Module – FBF	48	N/A	X X								
Pain Coping Strategies  Module – DB, GI, C, S	27	0.80- 0.88	X X	X XX	X X	X X	X X	X X	X X	X X	X X
Quantitative Sensory Testing 	13	0.94	X				X				X
Process factors:											
Self-efficacy Scale  Module – DB, GI, C, PN-BF, S,	6	0.91	X X	X XXX	X X	X X	X X	X X	X X	X X	X X
BF Self-Efficacy Scale  Module – FBF, BNPS, C, S, CPI	14	0.94	X XX	X X	X X	X X	X X	X X	X X	X X	X X
Index of Self-Regulation  Module – BNPS, DB, GI, C, S	9	0.73- 0.76	X XX	X XX	X X	X X	X X	X X	X X	X X	X X
Ongoing BF Assessment Survey Module  – FBF, BNPS, CPI	30	N/A	X XX	X X	X X	X X	X X	X X	X X	X X	X X
BF Algorithm  Module – FBF, BNPS, PN-BF	9	N/A	X XX	X X	X X	X X	X X	X X	X X	X X	X X
Maternal Assessment of Infant BF Behaviors  Module – FBF, BNPS, PN-BF	8	N/A	X XX	X X	X X	X X	X X	X X	X X	X X	X X
H&H Lactation Survey 	20	(0.75- 0.98)		X X	X X	X X	X X				
Proximal outcomes:											
PROMIS Anxiety, Sleep, Fatigue, Perceived Stress Scales  Module – DB, GI, C, S	6-30	0.79- 0.91		X X	X XX	X X	X X	X X	X X	X X	X X
Visual Analogue scale (0-100)  Module – BNPS, PN-BF	1	N/A	X X	X XX	X X	X X	X X	X X	X X	X X	X X
Edinburgh Postnatal Depression Scale  Module – C, S	10	0.87	X X	X X	X X	X X	X X	X X	X X	X X	X X
McGill Pain Scale  Module - BNPS, PN-BF	15	0.96	X X	X XX	X X	X X	X X	X X	X X	X X	X X
Brief Pain Inventory-SF  Module – BNPS, PN-BF	7	0.77- 0.91	X X	X XX	X X	X X	X X	X X	X X	X X	X X
Distal outcomes:											
Parenting Confidence Scale  Module – FBF, C, S	14	0.81	X X	X X	X X	X X	X X	X X	X X	X X	X X
PROMIS Global Physical Health and Mental Health  Module – GI, C, S	10	0.81- 0.86	X X	X X	X X	X X	X X	X X	X X	X X	X X

T1 = baseline; T2 = 1 week; T3 = 2 weeks; T4 = 3 weeks; T5 = 6 weeks;  
T6 = 9 weeks; T7 = 12 weeks; T8 = 18 weeks, T9 = 24 weeks

FBF = Fundamentals of BF; BNPS = BNP strategies; DB = Deep breathing;  
GI = Guided Imagery; PN-BF = Pain neurophysiology related to BF;  
C = Catastrophizing; S = Stress reactivity; CPI = Common pumping issues

shipping to [name] lab. Genomic DNA SNP genotyping will be completed for six SNPs, *COMT* (4 SNPs; (catechol-o-methyltransferase)), and *OXTR* (2 SNPs) (Table 3) using Taqman SNP genotyping assays (VIC/FAM) and allelic discrimination analysis according to manufacturer's directions using an Applied Biosystems StepOne Plus PCR machine and ABI allelic discrimination software (ThermoFisher Scientific, Waltham, MA). [name] has verified a < 95% call rate for all SNPs included using 10uL samples and manufacturer's running parameters.

**Whole Genome Methylation Sequencing.** The EZ DNA methylation Gold kit (Zymo Research) will be used for sodium bisulfite conversion of DNA prior to library preparation for DNA methylation of select pain sensitivity SNPs for 40 participants (5 zero and 15 highest pain phenotype per group). All libraries will be prepared using the TruSeq DNA Methylation (Illumina) method with 100 ng of converted gDNA per sample. Bisulfite-converted DNA will be first primed by random hexamers carrying a tag sequence on its 5' end. Subsequently, the bottom strand DNA will be extended and the 3' end annealed with another terminal-tagging oligo, which induces the synthesis of the 3' adaptors. Single-stranded DNA fragments with adaptors ligated will be purified and enriched by traditional PCR according to respective kits' instruction manuals. The resulting PCR products will be cleaned up and quality assessed by an Agilent 2100 Bioanalyzer. Before sequencing, the library will be spiked with other high-complexity sequences, according to the manufacturer's protocol to compensate for the reduced sequence diversity in bisulfite converted libraries. Finally, amplified DNA fragments will be quantified by qPCR or PicoGreen assay and sequenced on NovaSeq 6000 platform to generate 2 × 150 bp paired-end libraries.

SNP	Alleles	Frequency
COMT: Catechol-O-methyltransferase		
rs6269	G>A	0.36 (Global)
rs4633	C>T	0.37 (Global)
rs4818	G>C	0.30 (Global)
rs4680	A>G	0.37 (Global)
OXTR - oxytocin receptor		
rs2254298	G>A	0.21 (Global)
rs53576	G>A	0.31 (Global)

**Table 3. Gene Minor Allele Frequency**

### IFSMT Process Variables.

#### Knowledge and Beliefs.

**The Self-Efficacy for Managing Chronic Illnesses Scale.** The Self-Efficacy Scale is an NINR-recommended common data element adapted to manage BF pain.

**Breastfeeding Self-Efficacy Scale - Short Form.** The BSES-SF scores > 50 indicating greater maternal BF confidence and demonstrates sensitivity to maternal experience with BF, with BF self-efficacy at 1-week postpartum predicting BF methods at 4 and 8 weeks ( $p < 0.001$ ).

**Maternal Self-efficacy.** Karitane Parenting Confidence Scale measures maternal self-efficacy with good test-retest discriminant reliability ( $r(26) = .88$ ,  $p < 0.0001$ ), .81 internal consistency, and sensitivity and positive predictive power are 86% and 88%, respectively.

#### Self-Regulation Skills and Abilities.

**Index of Self-Regulation.** The Index of Self-Regulation is an NINR common data element used across several populations which assesses an individual's general behavior and change effort to make behavioral changes and modulate thoughts, emotions, and behaviors to achieve goals.

**Breastfeeding Algorithm.** An adaptation of the LATC scale, through texted UConn Health REDCap link women will assess daily (*BSM* intervention) or weekly (attention control) infant awake/sleep state, signs of hunger, number of attempts to latch, strength of latch and of suck, pattern of pauses and sucks, and time duration of BF sessions.

**Maternal Assessment of Infant BF Behaviors.** A clinical indicator of four infant BF behaviors based on the nursing personality assessment, maternal report, and digital recording of infant BF behaviors.

#### Social facilitation.

**Ongoing BF Assessment Survey.** Maternal self-report of BF experience, adequacy of milk supply, problem-solving BF challenges (BNP), use of pharmacological and non-pharmacological therapies and social support.

### IFSMT Proximal Outcomes.

#### Individual & Family Self-Management Behaviors.

**Acute BNP.** A visual analogue scale (0 - 100) used to measure BNP intensity during the last BF. Acute BNP will be measured with the short version of the Brief Pain Inventory. The Inventory has good reliability and validity with BNP. The Inventory has two subscales: pain intensity (4 items) and pain interference (7 items) and collects data on use of analgesics and of non-pharmacological measures. For initial data analysis, the average pain intensity and interference scores will be used, and other measures will be quantified. The McGill Pain Questionnaire short form is a reliable self-report measure of pain perception. It entails 15 verbal descriptors of sensory and affective dimensions of pain and is scored on a 4-point scale (0-none to 3-severe). Higher scores indicate higher levels of sensory and affective components of pain (range 0-45). Internal consistency reliability is in the excellent range for total pain score (Cronbach's alpha = 0.96).

**Cumulative BNP.** A score of acute BNP pain intensity from the VAS (0 - 100) at baseline, 1, 2, 3, 6, 9, 18, and 24 weeks will incrementally (baseline + 1 week, baseline + 1 and 2 weeks, etc.) be added together.

**NINR PROMIS Scales for Maternal Well-Being Symptoms.** The PROMIS scales of anxiety, perceived stress scale, sleep and fatigue. All PROMIS measures are based on the T-score (mean = 50, standard deviation = 10). In most cases 50 equals the mean in the U.S. general population.

**Edinburgh Postnatal Depression Scale.** Postnatal clinical screening tool for depressive symptoms with any score >10 indicates risk for depression and scores > 13 a depressive illness that requires referral. Women will be referred to their provider for fourth trimester care and may continue in the study. The scale has a sensitivity of 85%, specificity of 77% to identify women at high-risk for depression.

**H&H Lactation Survey.** A 20-item questionnaire maternal perception of milk supply with a 7-point Likert scale from 1 (strongly disagree) to 7 (strongly agree). Total scores ranged 20 ~ 140, with higher scores representing a higher perceived milk supply. The satiety subscale correlates with insufficient milk supply.

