### **Data Analysis and Management**

All data will be entered into a password-protected database stored on a firewall-protected server that is maintained by UConn. We will use the existing structure of data management established with our pilot study. The protocols established for trialing and monitoring UConn Health REDCap will be strictly followed. We have designed data collection forms to check for missing data in real-time to avoid incomplete data and routinely monitor data input. Our Project Manager, working with the statisticians, will prepare a weekly data summary, which will be reviewed during weekly team meetings.

**Statistical Analysis Overview.** Prior to undertaking statistical modeling, descriptive statistics will be determined for the study's key independent and dependent variables in order to evaluate the effectiveness of randomization, to check distributional assumptions (such as normality), to identify potential outlying observations, and to obtain preliminary insights into homogeneity versus heterogeneity of variance for outcome measures. Analyses will be conducted using SAS 9.4 and R^194.

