**SA1.** Initially, mixed effects linear modeling will be applied to contrast mean levels of pain at the 1-, 2-, and 3-week time points. The analyses will be repeated for a series of pain outcome measures, including BNP intensity, BNP interference, and cumulative BNP. The models will include “main” effects for intervention and time, an interaction between intervention and time, a random effect for “subject”, and the baseline value of the dependent variable as a covariate. Modeling results will be used to test for a time-by-intervention interaction. If the interaction is non-significant, the model will be re-fitted without it and testing will focus on the main effect of intervention. Regression diagnostics will be applied to all models to identify non-normality in residuals and potentially biasing effects of outlying observations. While mixed effects linear models are resistant to the impact of limited amounts of missing data, we will also utilize multiple imputation methods, as described below, to evaluate the sensitivity of model estimates and testing results to missing observations. Following evaluation of intervention effects at the 1-, 2-, and 3-week time points, we will proceed to assess differences in acute and cumulative BNP intensity and interference at 6, 9, 12, 18 and 24 weeks. Additionally, we will investigate whether subject-level “trends” or “growth curves” in pain levels across all eight study time points differ between the intervention and control conditions. If necessary, demographic variables will be included in the regression models both to account for potential confounding effects that might arise via imperfect randomization and to reduce unexplained between-subject variation in outcome variables.

**SA2. H2A.** We will start by investigating the intervention's effect on proportion of exclusive BF after week 6. Initially, the Pearson Chi-square test will be performed to detect the difference between intervention and control groups at 6, 9, 12, 18, and 24 weeks, respectively. Furthermore, a generalized linear mixed model with a logistic link will be applied to analyze the “main effect” of intervention and time, and “interaction effect” of intervention by time. The procedure to fit and re-fit the model will be similar to the approach for pain measures in SA1. The measure for BF self-efficacy, yield scale scores

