which range from 14-70. We will treat BF self-efficacy scores as "continuous" variable and follow the approach in SA1 to investigate the intervention effect on BF self-efficacy over time. **H2B.** Subsequently, we will assess intervention effects on maternal well-being - anxiety, depressive symptoms, fatigue, stress, and sleep disturbance over all the time points. Each of these variables' measurement scores will be treated as "continuous" and effects of the *BSM* intervention will be investigated following a similar approach as for the pain measures in SA1. Because these variables are highly interrelated, we will evaluate their response to intervention effects simultaneously. In this approach, differences in the quadrivariate means of these variables between the *BSM* and attention groups will be analyzed using multivariate mixed effects linear modeling in an approach analogous to that for the pain measures in SA1 but with the inclusion of covariances between random intercepts for the anxiety, depressive symptom, fatigue, and sleep disturbance scores at the subject level. Across the modeling procedures related to SA2, regression diagnostics will be applied to investigate suitability of distributional assumptions and potential biasing effects of outliers.

**SA3.** We will model effects of pain sensitivity SNPs on quantitative sensory testing measures, BNP intensity and interference, BF outcomes in SA2, and maternal and pain self-efficacy across all the time points. In addition, we will also assess the effects of individual quantitative sensory testing measures on all the outcome measures aforementioned over time. Analyses will utilize "linear/generalized linear" modeling with univariate and multivariate dependent variables, will account for correct temporal ordering among time varying measures, and will evaluate correlations between measures that jointly vary in time in response to other factors/covariates.

We have planned for attrition rates as high as 25%. However, our goal is to minimize attrition by instituting a participant outreach plan –namely, contacting participants to complete modules, providing monthly updates regarding child development, and encouraging women to remain involved. In statistical analyses, we will follow each model based only on "observed data" with sensitivity analyses in which Markov Chain Monte Carlo multiple imputation is used to assess the possibility and impact of "missing at random" data.

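### Cumulative BNP is a running sum, but SA1 gives it the acute-score model, which on the ordinary reading misstates its week-specific standard errors; its definition also omits week 12

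*Combined protocol and SAP*

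**What the plan says.** Under IFSMT Proximal Outcomes, cumulative BNP is built from VAS scores "at baseline, 1, 2, 3, 6, 9, 18, and 24 weeks will incrementally (baseline + 1 week, baseline + 1 and 2 weeks, etc". Baseline is a term in every sum, and week 12 is not listed.

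In Data Analysis and Management, SA1 starts with a mixed linear model for weeks 1, 2 and 3. It then states: "The analyses will be repeated for a series of pain outcome measures, including BNP intensity, BNP interference, and cumulative BNP". The terms are intervention, time, "an interaction between intervention and time, a random effect for" subject, and the baseline value of the outcome. No residual covariance is named. On testing: "If the interaction is non-significant, the model will be re-fitted without it and testing will focus on the main effect of intervention". What is read when the interaction is significant is not spelled out. SA1 continues: "we will proceed to assess differences in acute and cumulative BNP intensity and interference at 6, 9, 12, 18 and 24 weeks", and adds subject-level trends "in pain levels across all eight study time points differ between the intervention and control conditions".

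Two other places bear on the covariance. H2B describes its multivariate model as "in an approach analogous to that for the pain measures in SA1 but with the inclusion of covariances between random intercepts", which suggests that the SA1 subject effect is a random intercept. The Statistical Analysis Overview plans to obtain "preliminary insights into homogeneity versus heterogeneity of variance for outcome measures" before modelling.

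**The concern.** A random intercept with constant residual variance assumes one variance at all visits and one correlation between any two. A running sum cannot meet this, because each score is the previous one plus a new VAS. Its regression on baseline also steepens at each visit, while the model allows a single slope.

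H1 names cumulative BNP under the primary aim. A steady VAS benefit makes the cumulative difference widen by construction, so the interaction will usually be significant and week-specific contrasts are what remains to report. Those are the estimates whose standard errors the model gets wrong.

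The week-12 gap is a plain conflict between two parts of the text. SA1 asks for a comparison of a score that the definition does not supply.

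**Working it through.** **1. The plan's sample size.** For d = 0.39, 80% power and two-sided 5%: n = 2(1.960 + 0.842)²/0.39² = 103.2, so 104 per arm. Then 104/0.75 = 138.7, so 139 per arm, or 278 against 280 stated. It reproduces, and nothing below changes it.

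**2. Inputs.** From the plan: 140 per arm, d = 0.39, 25% loss at 24 weeks (140 × 0.75 = 105) and 6% pilot attrition (140 × 0.94 ≈ 131). The documents give no VAS SDs or correlations. Assumed: SD of 1 at each visit, common correlation r = 0.3, 0.5 or 0.7, complete data.

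**3. Variance and baseline slope.** At week w (w = 1, 2, 3) the sum has k = w + 1 terms.
- Variance: k + k(k − 1)r.
- Slope on baseline: 1 + wr.

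**4. Standard errors over weeks 1-3.** The single fitted slope is the average of the three, 1 + 2r. The week-w estimate is then an arm difference in (sum of w post-baseline scores − 2r × baseline). Its variance per woman is

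v_w = w + w(w − 1)r + 4r² − 4r²w.

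A random-intercept model reports the average of the three, v̄, at every week. The ratio of model to true SE is √(v̄/v_w).

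| r | variance, week 3 / week 1 | slope, weeks 1 to 3 | v_1, v_2, v_3 | v̄ | SE ratio, weeks 1, 2, 3 |
|---|---|---|---|---|---|
| 0.3 | 7.6/2.6 = 2.92 | 1.3 to 1.9 | 1.00, 2.24, 4.08 | 2.44 | 1.56, 1.04, 0.77 |
| 0.5 | 10/3 = 3.33 | 1.5 to 2.5 | 1.00, 2.00, 4.00 | 2.33 | 1.53, 1.08, 0.76 |
| 0.7 | 12.4/3.4 = 3.65 | 1.7 to 3.1 | 1.00, 1.44, 3.28 | 1.91 | 1.38, 1.15, 0.76 |

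Simulation agrees: about 1.4-1.6 at week 1 and 0.76-0.79 at week 3. A ratio of 0.76-0.77 turns 1.96 into 1.49-1.51 true SEs, which is 86-87% coverage. Simulated coverage was about 84-88% across runs.

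**5. No true effect** (20,000 simulated trials per setting; 105, 131 and 140 per arm).
- Interaction test: about 6.5-8% type I error.
- False week-3 claim when the interaction must be significant first: 5.0-5.7%, against 1.8-2.2% with a correct covariance.
- Any false claim: 8.2-9.4%, against 7.3-7.7% with a correct covariance.
- Pooled main effect: about 5%.

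**6. Constant 0.39 SD benefit** (105 and 131 per arm). The cumulative difference is 0.39 × w, that is 0.39, 0.78 and 1.17 VAS SDs. The interaction is significant in about 90-98% of trials. Week-3 coverage given a significant interaction is 88-91%. Some effect is found in about 99% of trials or more.

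**7. Falling VAS SD (also assumed).**
- A fall of 10-20% per visit: interaction error 6.7-8.0%, false week-3 claim 4.0-5.1%.
- A fall of 40% per visit: interaction error 6.5-8.1%, false week-3 claim 2.2-3.8%, week-3 coverage 90-93%.

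**8. Week 12.** Table 1 schedules the pain scales, which include the VAS, at week 12, and Table 2 lists the VAS at T7 (week 12). As defined, the week-18 sum has seven scores (0-700) and the week-24 sum eight (0-800). With week 12 they have eight (0-800) and nine (0-900). The pilot's sum used all four of its time points (0-400).

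**The case against.** The strongest reply is that the plan is silent on the covariance, not wrong about it. It looks at heterogeneity of variance before modelling, applies diagnostics to all models and mentions growth curves. A random slope would largely repair weeks 1-3 (interaction 4.6-5.1%, week-specific error 4.2-6.1%). This stands in part: the random-intercept reading is inferred. But the diagnostics named concern non-normality and outliers, and no step commits to a remedy.

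Second, the pilot reported a main effect for cumulative pain (d = 0.64, Justification of Sample Size) as well as week-specific differences, and the main-effect test holds its size. That is correct. However, SA1 reaches that test only if the interaction is non-significant, which a steady benefit makes unlikely.

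Third, equal SDs may overstate the week-3 distortion. That also stands, as step 7 shows.

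A reader might infer that week-3 findings carry a 13% false-positive rate. That figure (12.7-13.8%) applies only if week 3 is read whatever the interaction test shows, which SA1 does not plan. A reader might also infer that the primary analysis or the sample size is compromised. The acute VAS and interference models and N = 280 are untouched.

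**Conclusion.** Both parts hold, at limited weight.

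The week-12 conflict needs no assumption. The week-12 score is undefined, and the later totals depend on which section is followed.

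The covariance point is conditional on a random intercept with constant residual variance and on the assumptions in step 2. The direction follows from the definition of the score; the size depends on those assumptions. The main damage is to estimation: the week-1 standard error is too large, the week-3 one too small, and the week-3 interval too narrow. The effect on error rates is small. The false week-3 claim rate is about nominal (4-6%) under the interaction-first sequence, and the any-claim rate rises by at most about 2 points. Most of its excess over 5% comes from the two-step testing itself.

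The documents do not say whether one joint model would run to week 24, so no size is claimed for later weeks. Severity: minor to should-fix.

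**What to change.** 1. Reconcile the cumulative BNP definition with SA1 by adding week 12 to the list of weeks summed.
2. For cumulative BNP, specify an unstructured or heterogeneous-variance covariance with baseline-by-week terms. In simulation at 131 per arm, an unstructured covariance with these terms gave interaction error of 4.5-5.2% and week-specific error of 4.8-5.3%.
3. Name in advance the week-specific contrast to be read, for example week 3. Do not rely on the re-fitted main effect: under an unstructured covariance it leans heavily on week 1 and had only 44-57% power for a constant 0.39 SD benefit.

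The cost is one model statement, one named contrast and one corrected list, with no new data and no change to N. The downsides are a few more covariance parameters and slightly less favourable late-week p-values.

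An optional alternative is one prespecified summary per woman, such as mean VAS over weeks 1-3, compared by ANCOVA on baseline VAS. It avoids the covariance question but does not show timing, and it changes the outcome worded in H1, so it is a design decision and not a correction.
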